9 STUDY ACTIVITIES

9.1 Screening Period

Screening procedures (as detailed in [Appendix 1](#)) may begin once informed consent is obtained and will be used to establish subject eligibility and baseline characteristics for each subject. The Screening period for this study is up to 8 weeks to allow sufficient time for collection and analysis of sputum specimens. Subjects may be randomized as soon as all screening procedures have been performed and results have been received to verify eligibility criteria.

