10.2 Microbiology

10.2.1 Selection of Sample for Analysis

Sputum samples are collected at Screening, Baseline/Day 1, Day 28, Day 56 and Day 84/EOT. At least 2 and preferably 3 sputum samples are obtained at each time point. During Screening, samples will be collected after the subject signs the informed consent. For all subsequent visits, sputum samples should be collected on 2 to 3 consecutive days (when possible), just prior to, and up through the day of the scheduled visit.

The sputum specimens will be processed by a Central Specialty Microbiology Lab. Acid fast bacilli smear testing from sputum will be performed on all specimens received. Specimens will be further cultured in both solid and liquid media and identification of genus and species will be performed, to the subspecies level for *M. abscessus*.

In vitro susceptibility testing of antimicrobial drugs that may be used to treat *M. abscessus* pulmonary infection will be performed, and molecular characterization for select drug resistance markers will be performed.

Sputum samples noted to be of low volume will not be used for analysis unless all potential samples at a time point are of low volume. If all potential samples are of a low volume (signifying lower quality), the algorithms noted below for sample selection will be used.

For MIC susceptibility and outcome analyses of the MABC, the sample closest to but prior to the first dose of study drug (based on collection date and if on the same day as the first dose of study drug, collection date and time) which is positive for MABC is used as the baseline sample. If there are two samples positive for MABC with different subspecies, the one positive for *M. abscessus* subspecies *abscessus* is used. If multiple samples collected on the same day are positive for MABC, the sample positive for *M. abscessus* subspecies *abscessus* and with the highest MIC to omadacycline is considered the baseline sample. If the MICs are the same, the sample closest to the time of first dose of study drug based on time is used. The baseline samples for MAC and other species of mycobacterium (not *abscessus*) are defined in a similar manner and may or may not be the same sample as the one with MABC.

For post-baseline samples, a similar process is used for selecting the sample for analysis as that used for the baseline sample. The sample that is positive for MABC that is closest to the nominal/intended visit day should be selected.

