11.1 Efficacy Variables

The primary efficacy endpoints are:

- Clinical response (Definition 1) is defined as improvement at the Day 84 visit in severity of at least 50% of symptoms on the NTM Symptom Assessment Questionnaire present at baseline.

- Clinical response (Definition 2): is defined as improvement at the Day 84 visit in severity of at least 50% of symptoms on the NTM Symptom Assessment Questionnaire present at baseline and no deterioration in severity of any symptoms present at baseline.

Supportive analyses include analysis of clinical response (Definition 1 and Definition 2) at the Day 28 and Day 56 visits.

The secondary efficacy endpoints are:

- Change from baseline in Quality of Life - Bronchiectasis (QOL-B) domain scores at days 28, 56, 84, and Day 84/EOT
- Change from baseline in the St George's Respiratory Questionnaire (SGRQ) global and component scores at days 28, 56, 84, and Day 84/EOT
- Change from baseline in the Patient-reported Outcomes Measurement Information System (PROMIS) Fatigue 7a Short Form standardized score at days 28, 56, 84, and Day 84/EOT
- The Patient Global Impression – Change (PGI-C) response at days 28, 56, 84, and Day 84/EOT
- The Patient Global Impression – Severity (PGI-S) response at days 28, 56, 84, and Day 84/EOT
- The Clinical Global Impression – Improvement (CGI-I) response at days 28, 56, 84, and Day 84/EOT
- The Clinical Global Impression – Severity (CGI-S) response at days 28, 56, 84, and Day 84/EOT
- The percentage of subjects with a new symptom (defined as a symptom present post-baseline but absent at baseline) on the NTM Symptom Assessment Questionnaire with severity worse than mild at days 28, 56, 84, and Day 84/EOT
- The percentage of subjects with a decrease in quantitative MABC sputum culture from baseline to Day 84
- Time to growth in liquid medium only
- Time to first sputum culture negative for MABC

The additional efficacy endpoints are:

- Time to detection of MABC in growth media at baseline and the Day 28, 56, 84 and Day 84/EOT visits
- The percentage of subjects who convert from a positive MABC sputum culture at baseline to a sputum culture negative for MABC at any time post-baseline and at the Day 28, 56, 84 and Day 84/EOT visits
- In those subjects whose first negative culture (i.e., convert from a positive MABC sputum culture at baseline to a negative MABC sputum culture) is on the Day 28, 56, 84 and Day

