11.2 Baseline Values

Unless otherwise noted, baseline is defined as the last non missing value recorded before the first dose of test article. Unscheduled visits will be used in the determination of baseline values, when applicable.

For microbiologic analysis, see Section 10.3.1 for determination of the baseline sputum sample.

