12.2.9 Percentage of Subjects with a Decrease in Quantitative Mycobacterial Sputum

The ninth secondary efficacy endpoint is the percentage of subjects with a decrease in quantitative mycobacterial load from the sputum culture collected at the Day 84 visit and defined as a reduction in the semi-quantitative score (as defined in Table 10.3.2) as compared to baseline. The number and percentage of subjects with a reduction in the semi-quantitative score at the Day 84 visit will be presented for the ITT analysis set by treatment group. Exact 2-sided 95% CIs for the point estimate of the percentage of subjects with a decrease in each treatment group will be determined using the Clopper-Pearson method. The odds ratio (omadacycline relative to placebo) and p-value will be calculated using Cochran-Mantel-Haenszel test, stratified by prior antibiotic use. If the sample size is too small in one of the randomization stratification subgroups such that an adjusted analysis cannot be performed, an unadjusted analysis (chi-squared or Fisher's exact test) will be used.

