12.2.10 Time to Growth in Liquid Medium Only

Kaplan-Meier methods will be utilized to determine the time to growth in liquid medium only for MABC for the ITT Analysis Set by treatment group. The analysis will be limited to subjects with growth on agar plate at baseline in the ITT Analysis Set. Time to growth in liquid medium only will be defined as the number of days from the date of test article administration to the date of the first assessment where growth is detected in liquid medium only. If there is no sputum sample indicating growth in liquid medium only but there is a negative culture (defined in Section 12.2.11), the date of the first negative culture will be used for the determination of time to growth in liquid medium only.

Subjects who died, withdrew from the study, or received alternative antibiotic therapy (not including chronic macrolides) for treatment of the NTM infection prior to growth in liquid medium only for MABC (or a negative culture, if no sputum sample indicating growth in liquid medium only) will be censored at the date of the death, study withdrawal, or the start date of the alternative antibiotic therapy respectively. Subjects who have a positive sputum culture (defined as growth in both liquid medium and agar plate [growth on both LJ slant and biplate]) through Day 84 will be censored at the date of the Day 84 visit.

The median, 25th and 75th percentile for time to growth in liquid medium only will be provided with 2-sided 95% CIs for each treatment group. A p-value will be determined using a stratified (by prior antibiotic use) log-rank test. Kaplan-Meier curve for time to growth in liquid medium only will be provided in a figure.

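### The baseline for MABC outcome analyses is the last positive pre-dose sample, so a subject already negative on Day 1 and negative again later counts as converting on treatment

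*SAP*

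**What the plan says.** SAP 11.2 sets the general rule: "Unless otherwise noted, baseline is defined as the last non missing value recorded before the first dose of test article". It exempts microbiology and sends the reader to a separate rule. The section number it cites is 10.3.1, but the rule stands in 10.2.1.

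SAP 10.2.1 reads: "For MIC susceptibility and outcome analyses of the MABC, the sample closest to but prior to the first dose of study drug" (by collection date, and by time as well on the day of first dose) "which is positive for MABC is used as the baseline sample". The scope is explicit: MIC and outcome.

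Four microbiological analyses matter here:

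- **Conversion (11.1, 12.3):** subjects who "convert from a positive MABC sputum culture at baseline to a sputum culture negative for MABC at any time post-baseline", and also by visit.
- **Decrease in load (12.2.9):** "defined as a reduction in the semi-quantitative score" at Day 84 compared with baseline.
- **Time to growth in liquid medium only (12.2.10):** "The analysis will be limited to subjects with growth on agar plate at baseline in the ITT Analysis Set". A first negative culture serves as the event if no liquid-only sample exists.
- **Time to first negative culture (12.2.11):** days from first dose to the first MABC-negative culture in the ITT set. No baseline sample enters the definition.

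The protocol requires a positive culture at Screening (6.2, criterion 3) but none on Day 1. Sputum is collected again at the Day 1 visit before dosing (Appendix 1). Screening may last 56 days (5.1), and the reason given is: "The Screening period for this study is up to 8 weeks to allow sufficient time for collection and analysis of sputum specimens".

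**The concern.** The last-positive rule suits MIC, subspecies and resistance, because those need an isolate. An outcome baseline should describe the subject's state when treatment starts. Entry guarantees a Screening positive, so in an eligible subject the rule can always find a positive baseline, even when every Day 1 specimen shows no growth. A change that took place between Screening and Day 1 can then be reported as a change on treatment.

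At stake are the second secondary objective, microbiological response, and the placebo conversion rate, which has value of its own in this disease. No section excludes, reclassifies or tabulates the Screening-positive, Day 1-negative subjects. They can be found only in the listings of all samples.

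**Working it through.** **1. Tracing one subject.** Take a Screening sample with agar growth (score 4, say), no growth on any Day 1 specimen, and no growth at Day 28 or Day 84.

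| Analysis | Result under the SAP | Last change in status seen |
|---|---|---|
| Conversion (11.1, 12.3) | converter | before dosing |
| 12.2.9 | decrease, 4 to 0 | before dosing |
| 12.2.10 | in the set (Screening agar growth), event at Day 28 | before dosing |
| 12.2.11 | event at Day 28, whatever 10.2.1 says | before dosing |

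Two further consequences follow from the text.

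- If the same subject had a Day 84 score of 2, 12.2.9 would still record a decrease (4 to 2), although the score rose from the Day 1 value of 0.
- A subject whose Day 1 specimens grow only in broth is positive (12.3), so that sample is the baseline. The score is 1 and the subject is outside the 12.2.10 set. A subject with no growth at all on Day 1 is inside that set, on the Screening sample. The lower Day 1 burden receives the higher baseline.

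**2. The plan's own figure.** The only design calculation is power for clinical response: 15% against 45%, 30 and 45 subjects, two-sided 0.05. It reproduces (0.799 by normal approximation, 0.802 by exact enumeration of the Mantel-Haenszel test, against about 80%). It does not bear on this point.

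**3. Size, on assumed inputs.** Let f be the Day 1-negative fraction, c the conversion rate among Day 1-positives, and s the probability that a Day 1-negative subject is negative at the later visit. None of these is in the documents.

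Reported rate = (1 − f)·c + f·s

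The part f·s is not a change from Day 1. Counted over all subjects, the overstatement is f·s. Against the rate in Day 1-positives it is f·(s − c), which is positive whenever s exceeds c.

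Take c = 40% on omadacycline and 10% on placebo, so the odds ratio is (0.40/0.60)/(0.10/0.90) = 6.0. With s = 0.8 on omadacycline and 0.6 to 0.8 on placebo:

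| f | Omadacycline | Placebo | Odds ratio |
|---|---|---|---|
| 5% | 42% | 12.5–13.5% | 5.1–4.6 |
| 10% | 44% | 15–17% | 4.5–3.8 |
| 15% | 46% | 17.5–20.5% | 4.0–3.3 |

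At f = 10%, the Day 1-negatives counted as converters would be 45 × 0.10 × 0.8 = 3.6 on omadacycline and 30 × 0.10 × 0.6 to 0.8 = 1.8 to 2.4 on placebo.

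**4. The direction for the odds ratio is not fixed.** Keep f = 10% and vary s:

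| s omadacycline | s placebo | Reported rates | Odds ratio |
|---|---|---|---|
| 0.8 | 0.8 | 44% v 17% | 3.8 |
| 0.8 | 0.4 | 44% v 13% | 5.3 |
| 0.4 | 0.1 | 40% v 10% | 6.0 |
| 0.9 | 0.2 | 45% v 11% | 6.6 |

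**5. Fluctuation alone.** Suppose no drug effect, and a per-visit chance of a negative set that varies between subjects (beta, mean 10% to 30%, concentration 2 to 5). Any-time conversion is then 14.9% to 52.1% under the SAP rule and 11.8% to 46.8% among Day 1-positives. Of the apparent converters, 19% to 35% were already negative on Day 1.

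**The case against.** The rule is prespecified, uses only pre-dose data and is the same in both arms. Entry needs two positive cultures at least 30 days apart, so one negative Day 1 set does not show clearance; such a subject may still be infected. That is fair, but the SAP counts a single negative visit after dosing as conversion. The same observation is passed over before the dose and credited after it.

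Post-baseline selection also prefers positives, so every usable specimen at a later visit must be negative, or no sputum produced (protocol 8.10 counts that as negative). This stands, and it limits the number affected. It works within one visit, however, while the baseline rule can reach back over a whole negative visit. Eight weeks is also a maximum: randomisation may follow as soon as results arrive.

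Sampling error is larger than the shifts shown. For 18/45 against 3/30, the log odds ratio has standard error √(1/18 + 1/27 + 1/3 + 1/27) = 0.68, giving an approximate 95% interval of 1.6 to 23 around 6.0. The endpoints are secondary or additional, p-values are nominal, and the symptom-based primary endpoint is untouched. All of this stands and bounds the importance.

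Four stronger readings are tempting, and the documents do not support them:

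- *Every Day 1-negative subject is a converter.* A negative post-baseline visit is also required.
- *The rule necessarily pulls the comparison toward no effect.* Step 4 shows that this depends on persistence in each arm.
- *The rule favours omadacycline or raises the type I error.* It uses pre-dose data identically in both arms.
- *The 10.2.1 rule creates the events in 12.2.11.* That analysis uses no baseline sample. It counts Day 1-negatives because it does not condition on Day 1 status.

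**Conclusion.** The point holds as a defect of definition. For conversion, 12.2.9 and 12.2.10, the outcome baseline can be a Screening sample up to eight weeks old although later pre-dose specimens were negative. Negative status that predates dosing is then reported as on-treatment change, which overstates the absolute rates in both arms. Section 12.2.11 has the same weakness by a different route.

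The size cannot be fixed from the documents. With 5% to 15% Day 1-negatives who mostly stay negative in both arms, the assumed omadacycline rate rises by 2 to 6 points and the placebo rate by 2.5 to 10.5 points, and an odds ratio of 6.0 falls to between 5.1 and 3.3. Dilution is conditional on that persistence. The reading of the text is firm; the numerical impact is illustrative.

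**What to change.** 1. In SAP 10.2.1, keep the last-positive rule for MIC, subspecies and resistance.
2. Derive a Day 1 culture status and semi-quantitative score from the Day 1 visit specimens, with the any-positive visit rule. Fall back to Screening only if no Day 1 specimen is evaluable.
3. Tabulate Screening-positive, Day 1-negative subjects by arm.
4. Report the conversion analyses, 12.2.9, 12.2.10 and 12.2.11 also in subjects MABC-positive on Day 1. For 12.2.10 require agar growth on Day 1; for 12.2.9 use the Day 1 score as baseline.
5. Keep the ITT analyses beside these. Protocol 12.5.2.2 specifies the ITT set for all three microbiological secondary endpoints, so removing Day 1-negatives from them would depart from the protocol.
6. Correct the cross-reference in SAP 11.2 to 10.2.1.

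The cost is SAP wording, one derived status and score from data already collected, a slightly smaller set for the added analyses, and a few extra tables. Day 1 status is pre-dose, so the restriction brings no treatment-related selection. If the blind has already been broken, the added analyses can still be reported, labelled post hoc as SAP section 6 requires.

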10.2.2 Baseline Analyses

The following will be provided for the baseline MABC specimen:

- Baseline positive culture for MABC and by subspecies, as well as MAC and other mycobacterium.
- Distribution of the semi-quantitative score defined as follows:

Semi-quantitative culture scores	Growth in broth	Growth on agar plate	CFU/mL on an agar plate
0	-	-	0
1	+	-	0
2	+/-	+	1 - <50
3	+/-	+	50-99
4	+/-	+	100-199
5	+/-	+	200-299
6	+/-	+	≥300

- Distribution of MIC to amikacin, cefoxitin, ciprofloxacin, clarithromycin, clarithromycin-D14, clofazimine, doxycycline, imipenem, linezolid, minocycline, moxifloxacin, omadacycline, tigecycline, and trimethoprim/sulfamethoxazole
- Susceptibility profile (interpreted as resistant, susceptible and intermediate according to CLSI breakpoints) to each antibiotic with defined breakpoints
- Multidrug Resistance (MDR) defined as nonsusceptibility (MIC value interpreted as “I” or “R”) to at least one agent in three or more antimicrobial categories. Agents that do not have susceptibility interpretations i.e. those in Table 10.3.2 with ‘N/A’ will not be considered in this analysis.
- MIC range, MIC₅₀ and MIC₉₀ to omadacycline

Table 10.3.2. Antimicrobial Categories, Agents and CLSI Breakpoints

Antimicrobial Category for MDR evaluation	Antimicrobial Agent	MIC ug/mL		
		S	I	R
Aminoglycoside	Amikacin	≤16	32	≥64
Cephalosporin	Cefoxitin	≤16	32-64	≥128
Fluoroquinolone	Ciprofloxacin	≤1	2	≥4
Macrolide	Clarithromycin	≤2	4	≥8
N/A	Clofazimine	N/A	N/A	N/A
Tetracycline	Doxycycline	≤1	2-4	≥8
Carbapenem	Imipenem	≤4	8-16	≥32
Oxazolidinone	Linezolid	≤8	16	≥32

N/A	Minocycline	N/A	N/A	N/A
Fluoroquinolone	Moxifloxacin	≤1	2	≥4
Antifolate	Trimethoprim-sulfamethoxazole	≤2/38		≥4/76
N/A	Tigecycline	N/A	N/A	N/A

S=Susceptible, I=Intermediate, R=Resistant

Clinical and Laboratory Standards Institute. Performance Standards for Susceptibility Testing of Mycobacteria, Nocardia spp., and Other Aerobic Actinomycetes 1st ed. CLSI document M62. 2018. CLSI, [name].

Microbiology results will be incorporated into several of the efficacy analyses, as defined in Section 11.1.

The by-subject listings noted below will also be provided. On each listing, all samples will be presented and the baseline and post-baseline samples selected as indicated above will be indicated with a flag.

- Decreasing susceptibility (defined as a greater than 4-fold increase in MIC to a given antimicrobial agent from the baseline sample to the post-baseline sample) at any visit. The listing will show the MICs for all antimicrobials, including those that do not show decreasing susceptibility
- Drug resistance markers at all visits
- Smear results at all visits
- Colony count data including CFU count and grouped CFU count (1-49, 50-100, >100-200, >200-500

A listing of MIC data for all samples will also be provided as will a listing of all other results for all samples.

11. EFFICACY ANALYSES

The primary and secondary efficacy analyses will be based on the ITT analysis set. Supportive efficacy analyses will be performed using the PP analysis set.

11.1 Efficacy Variables

The primary efficacy endpoints are:

- Clinical response (Definition 1) is defined as improvement at the Day 84 visit in severity of at least 50% of symptoms on the NTM Symptom Assessment Questionnaire present at baseline.

- Clinical response (Definition 2): is defined as improvement at the Day 84 visit in severity of at least 50% of symptoms on the NTM Symptom Assessment Questionnaire present at baseline and no deterioration in severity of any symptoms present at baseline.

Supportive analyses include analysis of clinical response (Definition 1 and Definition 2) at the Day 28 and Day 56 visits.

The secondary efficacy endpoints are:

- Change from baseline in Quality of Life - Bronchiectasis (QOL-B) domain scores at days 28, 56, 84, and Day 84/EOT
- Change from baseline in the St George's Respiratory Questionnaire (SGRQ) global and component scores at days 28, 56, 84, and Day 84/EOT
- Change from baseline in the Patient-reported Outcomes Measurement Information System (PROMIS) Fatigue 7a Short Form standardized score at days 28, 56, 84, and Day 84/EOT
- The Patient Global Impression – Change (PGI-C) response at days 28, 56, 84, and Day 84/EOT
- The Patient Global Impression – Severity (PGI-S) response at days 28, 56, 84, and Day 84/EOT
- The Clinical Global Impression – Improvement (CGI-I) response at days 28, 56, 84, and Day 84/EOT
- The Clinical Global Impression – Severity (CGI-S) response at days 28, 56, 84, and Day 84/EOT
- The percentage of subjects with a new symptom (defined as a symptom present post-baseline but absent at baseline) on the NTM Symptom Assessment Questionnaire with severity worse than mild at days 28, 56, 84, and Day 84/EOT
- The percentage of subjects with a decrease in quantitative MABC sputum culture from baseline to Day 84
- Time to growth in liquid medium only
- Time to first sputum culture negative for MABC

The additional efficacy endpoints are:

- Time to detection of MABC in growth media at baseline and the Day 28, 56, 84 and Day 84/EOT visits
- The percentage of subjects who convert from a positive MABC sputum culture at baseline to a sputum culture negative for MABC at any time post-baseline and at the Day 28, 56, 84 and Day 84/EOT visits
- In those subjects whose first negative culture (i.e., convert from a positive MABC sputum culture at baseline to a negative MABC sputum culture) is on the Day 28, 56, 84 and Day

84/EOT visits, the number and percentage of subjects with a culture positive for *M. avium* or other non-abscessus mycobacterium species at baseline

- The percentage of subjects who convert from a positive MABC culture at baseline to a sputum culture negative for MABC post-baseline (through the Day 56 visit) and have no subsequent positive MABC sputum culture during the study
- The number and percentage of subjects who convert from a positive MABC sputum culture at baseline to a sputum culture negative for MABC or with MABC growth only in liquid medium at any time post-baseline and at the Day 28, 56, 84 and Day 84/EOT visits
- Quantitative mycobacterial load (CFU/mL) and semi-quantitative score of the MABC at baseline and the Day 28, 56, 84 and Day 84/EOT visits

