8.21 Subject Discontinuation or Withdrawal

Reasons why a subject may discontinue or be withdrawn from the study include, but are not limited to, AE, worsening of disease under study, lost to follow up, withdrawal by subject, physician decision, death, and other (specify reason eg, subject non-compliance or study termination by the sponsor). Subjects may voluntarily withdraw from the study for any reason at any time. Subjects are considered withdrawn from the study if they state an intention to withdraw, or fail to return for visits, or become lost to follow up for any other reason. In the event a subject is lost to follow-up, every possible effort should be made to contact the subject and determine the reason for discontinuation as local law permits. The due diligence measures taken must be documented in the subject's source documents. If premature withdrawal from the study occurs, the investigator should determine the primary reason for a subject's premature withdrawal from the study and record the date and primary reason on the eCRF. Subjects who discontinue study treatment prematurely should complete the EOT visit and Safety Follow-up assessment, if possible (see Schedule of Assessments – [Appendix 1](#)). Exceptions to this include subjects who withdraw consent or are considered lost to follow-up after appropriate due diligence measures have been taken.

Site personnel must also contact the IxRS to register the subject's discontinuation from test article.

For subjects who are lost to follow up, the investigator should show "due diligence" by documenting in the source documents the steps taken to contact the subject (eg, dates of telephone calls, registered letters, etc).

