9.3 Follow-up Period

9.3.1 30-Day Safety Follow-up Call

The Follow-up assessment should be conducted 30 to 37 days following the subject's last dose of test article to assess safety via review of AEs and concomitant medications. This evaluation should also be conducted for any prematurely withdrawn subject except for subjects who withdraw consent or are lost to follow up. The Follow-up assessment may be conducted via telephone or at the investigator's discretion, the safety follow-up can be an office visit.

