11.4 Handling of Dropouts or Missing Data

Data imputation methods for the primary endpoint and other analyses for the primary endpoint are described in Section 11.1.

No imputations will be made for missing values for secondary endpoints. Summaries for these endpoints will be based on observed data only.

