12.3 Additional Efficacy Analyses

- Time to detection of MABC (in days) in liquid growth medium at baseline and the Day 28, 56, 84 and Day 84/EOT visits will be summarized by treatment group, including n, mean, SDs, median, minimum and maximum.
- The number and percentage of subjects who convert from a positive MABC sputum culture at baseline to a sputum culture negative for MABC at any time post-baseline and at the Day 28, 56, 84 and Day 84/EOT visits and who do not convert to a negative culture (i.e., remain positive) will be summarized by treatment group.
- In those subjects whose first negative culture (i.e., convert from a positive MABC culture at baseline to a negative MABC culture) is on the Day 28, 56, 84 and Day 84/EOT visits, the number and percentage of subjects with a culture positive for *M. avium* or other non-abscessus mycobacterium species at baseline and at the visit will be summarized by treatment group.
- The number and percentage of subjects who convert from a positive MABC culture at baseline to a sputum culture negative for MABC by the Day 56 visit and have no subsequent positive MABC culture will be presented, as well as the number and percentage of subjects who convert to a negative culture by the Day 56 visit and have a subsequent positive culture, and those who do not convert to a negative culture by Day 56 will be summarized by treatment group.
- The number and percentage of subjects who convert from a positive MABC sputum culture at baseline to a sputum culture negative for MABC or growth of MABC only in liquid medium at any time post-baseline and at the Day 28, 56, 84 and Day 84/EOT visits and who do not convert to a negative culture will be summarized by treatment group.
- The number and percentage of subjects whose first negative culture (i.e., convert from a positive MABC culture at baseline to a negative MABC culture) is on the Day 28, 56, 84 and Day 84/EOT visits will be summarized by treatment group.
- A shift table of the semi-quantitative score from baseline to Days 28, 56, 84 and EOT visits will be presented by treatment group.
- Quantitative mycobacterial load (CFU/mL) and semi-quantitative score of the MABC at baseline and the Day 28, 56, 84 and Day 84/EOT visits will be summarized by treatment group, including including n, mean, SDs, median, minimum, and maximum, geometric mean, 95% CI of geometric mean, and %CV for mycobacterial load and number and percentage of subject of each semi-quantitative score.

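### The count of subjects converted by Day 56 with no later positive culture includes converters who were never cultured again

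*SAP*

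**What the plan says.** SAP 11.1 puts this endpoint among the additional ones, after the primary and secondary lists. It is the percentage of subjects, culture-positive for MABC at baseline, who become negative after baseline. The window and condition are "through the Day 56 visit) and have no subsequent positive MABC sputum culture during the study".

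SAP 12.3 turns this into three counts by arm:

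- subjects who become "negative for MABC by the Day 56 visit and have no subsequent positive MABC culture will be presented";
- subjects "who convert to a negative culture by the Day 56 visit and have a subsequent positive culture";
- "those who do not convert to a negative culture by Day 56 will be summarized by treatment group".

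No test or confidence interval is specified. By default the denominator is every subject in the arm (SAP 6).

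Sputum is scheduled at Screening, Baseline, Day 28, Day 56 and Day 84/EOT (SAP 10.2.1; Protocol Appendix 1). For early stoppers, Protocol 8.21 says: "Subjects who discontinue study treatment prematurely should complete the EOT visit and Safety Follow-up assessment, if possible". It exempts those who withdraw consent or are lost to follow-up. The contact about 30 days after the last dose (Protocol 9.3.1) is "to assess safety via review of AEs and concomitant medications"; no sputum is scheduled then.

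**The concern.** The condition is that no later positive exists, not that a later negative does. A converter with no culture after the first negative satisfies it automatically, and of the three categories in SAP 12.3 only the first can hold that subject.

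The Day 56 cut-off leaves out subjects first negative at Day 84, who have no later scheduled culture. That suggests the row is meant to say something about persistence. A converter lost before any later culture is in the same position but is counted.

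This is also the only planned tabulation that follows a conversion forward within the subject. If one arm loses more later cultures than the other, its percentage gains from that loss. Protocol 3.2 says no earlier clinical trial of the drug dosed beyond 14 days, so discontinuation over 84 days is hard to predict.

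**Working it through.** **1. Does another rule remove these subjects?**

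- SAP 11.4: "No imputations will be made for missing values for secondary endpoints". This rule, and the similar one in SAP 12.2, is written for secondary endpoints. Carried over to this endpoint it would change nothing, because no later positive would be observed.
- SAP 12.1.1 and 12.1.2 score early discontinuation or a missing Day 84 assessment as non-response, for the primary endpoint only.
- SAP 12.2.11 censors subjects only for events before the first negative culture.
- Protocol 8.10 scores a post-baseline visit as negative if the subject cannot produce sputum. It does not cover a visit that never took place.

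None applies.

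**2. Culture histories under the wording of SAP 11.1 and 12.3**

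| History | Category | Later culture? |
|---|---|---|
| Negative at Days 28, 56 and 84 | No later positive | Yes |
| Negative at Day 28, then withdrawn | No later positive | **None** |
| First negative at an early EOT visit on or before Day 56 | No later positive | **None scheduled** |
| First negative at Day 56, Day 84 missing | No later positive | **None** |
| Negative at Day 28, stops, EOT negative | No later positive | Yes |
| Negative at Day 28, stops, EOT positive | Later positive | Yes |

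The three bold rows are pooled with the first. The last two rows are handled properly.

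**3. Size**

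The plan gives no figure for this endpoint. Its one design figure is about 80% power for the primary endpoint (SAP 5). It reproduces: with 30 and 45 subjects, 15% and 45%, the pooled rate is (4.5 + 20.25)/75 = 0.33, and power = Φ[(0.30 − 1.96 × √(0.33 × 0.67 × (1/30 + 1/45))) / √(0.15 × 0.85/30 + 0.45 × 0.55/45)] = 79.9%. It has no bearing here.

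All rates below are assumptions. Let *c* be the share converting by Day 56, *r* the share of converters who relapse, and *d* the share of converters with no later culture. Relapse is taken to be equally common with and without a later culture.

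- True percentage: c(1 − r)
- As written: c[(1 − d)(1 − r) + d], an error of +c·d·r
- Unconfirmed converters counted as failures: c(1 − d)(1 − r), an error of −c·d·(1 − r)

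Omadacycline arm (N = 45, c = 40%, so 18 converters):

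| r | d | True | As written | Counted as failures |
|---|---|---|---|---|
| 30% | 10% | 28.0% | 29.2% | 25.2% |
| 30% | 20% | 28.0% | 30.4% | 22.4% |
| 30% | 30% | 28.0% | 31.6% | 19.6% |
| 50% | 20% | 20.0% | 24.0% | 16.0% |
| 50% | 30% | 20.0% | 26.0% | 14.0% |

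Arms compared with no true difference (c = 40%, r = 40%, true value 24.0% in both):

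| d, omadacycline / placebo | As written | Difference | Counted as failures | Difference |
|---|---|---|---|---|
| 10% / 10% | 25.6% / 25.6% | 0 | 21.6% / 21.6% | 0 |
| 20% / 10% | 27.2% / 25.6% | +1.6 | 19.2% / 21.6% | −2.4 |
| 30% / 10% | 28.8% / 25.6% | +3.2 | 16.8% / 21.6% | −4.8 |

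In the last row, 18 × 0.30 = 5.4 omadacycline converters are unconfirmed, but only 5.4 × 0.40 = 2.16 (4.8 points of 45) are misclassified. On placebo it is 12 × 0.10 × 0.40 = 0.48 (1.6 points of 30). The gap is 4.8 − 1.6 = 3.2 points.

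**The case against.** The strongest reply is that this is one of several additional endpoints, counted by arm without a test, in a study the SAP calls exploratory. The SAP labels the row literally and never calls these subjects sustained or durable converters. Conversion by visit, semi-quantitative shift tables and by-subject listings are also planned, so unconfirmed converters could be found. All of this stands and limits the importance of the point. It does not mend the row, which gives no sign that it mixes confirmed and unconfirmed converters.

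Three stronger readings are tempting, and the documents do not support them.

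- *A reader might infer that anyone who stops early cannot fail.* Early stoppers are asked for an EOT visit, and sputum is collected there. A positive EOT culture after an earlier negative moves the subject to the second category.
- *A reader might infer a large gap between arms.* Suppose 9 of 45 omadacycline subjects stop early with half negative at last culture (4.5 subjects, 10 points), and 3 of 30 placebo subjects stop with 10–20% negative (0.3–0.6 subjects, 1–2 points). That suggests 8–9 points. But it treats every unconfirmed converter as a false one and every negative last culture as unconfirmed. It also builds in different negativity by arm, which would be drug effect rather than artefact. With half negative in both arms the unconfirmed shares are 10 and 5 points. At 30–50% relapse, the misclassified part of that 5-point gap is 1.5–2.5 points.
- *A reader might infer that counting these subjects as failures removes the bias.* It reverses it: −4.8 instead of +3.2 in the no-difference example. At 30% relapse its error is 0.7/0.3, or about 2.3 times, the error as written.

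**Conclusion.** The point holds in limited form. The stated rule classes converters with no culture after their first negative together with those whose later cultures stayed negative, and no other rule separates them. The percentage is inflated by unconfirmed converters, and the arm comparison is distorted if loss of later cultures differs by arm. Only those unconfirmed converters who would have relapsed are truly misclassified.

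Size and direction cannot be found from the documents, which give no conversion, relapse or dropout rates. Under the assumed rates above, the artefact between arms is 0 with equal loss, 1.6 points at 20% against 10%, and 3.2 points at 30% against 10%. The primary and secondary analyses and the sample size are unaffected.

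**What to change.** In SAP 11.1 and 12.3:

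1. Limit the first category to converters by Day 56 with at least one later culture result, all of them negative. Say that an EOT culture after the first negative qualifies, and that another specimen from the same visit does not.
2. State whether a visit without sputum, scored negative under Protocol 8.10, counts as a later result.
3. Add a fourth category, shown by arm, for subjects converted by Day 56 with no later culture.
4. Report the percentage with the fourth category counted as success and again as failure, as bounds for each arm, rather than only as failure. Bounds for the difference pair one arm's upper value with the other's lower. In the 30% against 10% example these are 28.8 − 21.6 = +7.2 and 16.8 − 25.6 = −8.8 points.

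The cost is a few sentences and one more table row, from data already collected, and a lower headline percentage. If the blind has already been broken, the row can still be added and labelled post hoc, as SAP 6 requires.
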